13.1.6 CGI-S

The CGI-S score change from Baseline at each post-Baseline timepoint will be analyzed using an MMRM model similar to that used for the primary efficacy endpoint. The dependent variable will be the CGI-S score change from Baseline, and the independent variables in the model will include the following: visit (Weeks 2, 4, 6, and 8), Baseline CGI-S score (continuous covariate), and Baseline CGI-S score-by-visit interaction.

13.1.7 CGI-I

The CGI-I score at each post-Baseline timepoint will be analyzed using an MMRM model similar to that used for the primary efficacy endpoint. The dependent variable will be the CGI-I score, and the independent variables in the model will include the following: visit (Weeks 2, 4, 6, and 8), Baseline CGI-S score (continuous covariate), and Baseline CGI-S score-by-visit interaction.

The CGI-I scores will also be dichotomized by combining scores of 1 or 2 (very much improved or much improved) into an “Improved” category, and all remaining scores into a “Not Improved” category. At each timepoint, the proportion of responders (very much improved or much improved) will be descriptively summarized including 95% confidence intervals. Both OC, in which subjects with missing values at a given visit are excluded, as well as missing values imputed as not improved, will be presented.

The observed (un-dichotomized) scores, as well as dichotomized scores, will be descriptively summarized by visit.

13.1.8 SCOPA

13.1.8.1 SCOPA-NS

The SCOPA-NS score at each post-Baseline timepoint will be analyzed using an MMRM model similar to that used for the primary efficacy endpoint. The dependent variable will be

the SCOPA-NS score change from baseline, and the independent variables in the model will include the following: visit (Weeks 4 and 8), Baseline SCOPA-NS score (continuous covariate), and Baseline SCOPA-NS score-by-visit interaction.

13.1.8.2 SCOPA-DS

The SCOPA-DS score at each post-Baseline timepoint will be analyzed using an MMRM model similar to that used for the primary efficacy endpoint. The dependent variable will be the SCOPA-DS score change from Baseline, and the independent variables in the model will include the following: visit (Weeks 4 and 8), Baseline SCOPA-DS score (continuous covariate), and Baseline SCOPA-DS score-by-visit interaction.

13.1.8.3 SCOPA Global Sleep Quality

The SCOPA global sleep quality score at each post-Baseline timepoint will be analyzed using an MMRM model similar to that used for the primary efficacy endpoint. The dependent variable will be the global sleep quality score change from Baseline, and the independent variables in the model will include the following: visit (Weeks 4 and 8), Baseline global sleep quality score (continuous covariate), and Baseline global sleep quality score-by-visit interaction.

13.1.9 EQ-5D-5L

13.1.9.1 EQ-5D-5L Descriptive System

For each EQ-5D-5L dimension the proportion of subjects reporting no, slight, moderate, severe, and extreme/unable to perform activity will be summarized descriptively at each timepoint (Baseline, Week 4, and Week 8), using both OC and LOCF analysis methods.

Change from Baseline in EQ-5D-5L health state will be assessed with the Pareto classification of health change (PCHC) method. By using this methodology, at each post-Baseline visit (Week 4 and Week 8), each EQ-5D-5L health state will be classified into one of four categories, relative to the Baseline health state:

- Improved = improved on at least one dimension and not worsened on any other dimension
- Mixed = improved on at least one dimension and worsened on at least one other dimension
- No change = no changes in any dimension
- Worsened = deterioration on at least one dimension and no improvement on any other dimension

The proportion of subjects in each PCHC category will be summarized descriptively at Week 4 and Week 8, using both OC and LOCF analysis methods.

13.1.9.2 EQ-5D-5L VAS

EQ-5D-5L VAS score change from Baseline at each post-Baseline timepoint will be analyzed by using an MMRM model similar to that used for the primary efficacy endpoint. The dependent variable will be the EQ-5D-5L VAS change from Baseline, and the independent variables in the model will include the following: visit (Weeks 4 and 8), Baseline EQ-5D-5L VAS score (continuous covariate), and Baseline EQ-5D-5L VAS score-by-visit interaction.

13.1.9.3 EQ-5D-5L Index Scores

Since a United States value set to map EQ-5D-5L health states to preference weights (i.e., index values) is not yet available, the EQ-5D-5L index scores will be derived from EQ-5D-3L values. This procedure entails using a crosswalk dataset to map health states from the 5L system to the 3L system, and then applying EQ-5D-5L-3L weights from the US general population to obtain the index scores. The SAS software program to assign each health state to its corresponding index score was obtained from the EuroQol Research Foundation.

The EQ-5D-5L index score change from Baseline at each post-Baseline timepoint will be analyzed using an MMRM model similar to that used for the EQ-5D-5L VAS.

13.1.10 LOCF ANCOVA for Continuous Efficacy Variables

For each of the continuous secondary efficacy endpoints (HAMD-17, CGI-S, CGI-I, SCOPA-NS, SCOPA-DS, SCOPA global sleep quality, EQ-5D-5L VAS, EQ-5D-5L index scores), ANCOVA using LOCF will be performed at each post-baseline visit, similar to that described in Section 13.1.2.

To assess whether there is a linear correlation between the HAMD-17 total score change from Baseline and CGI-I rating, the HAMD-17 total score change from Baseline will also be summarized by CGI-I rating for all post-baseline visits. The mean \pm SE HAMD-17 total score change from Baseline by CGI-I rating will also be plotted for Week 8OC.

14 SAFETY ANALYSES

The safety analysis will be performed based on the Safety Analysis Set using actual treatment. Safety variables include adverse events (AEs), clinical laboratory variables, vital signs, body weight, BMI, physical examinations, electrocardiogram (ECG), C-SSRS, MMSE, and MDS-UPDRS Part III variables.

14.1 Adverse Events

All Adverse events (AEs) will be coded using MedDRA version 19.0 or newer.

An AE (classified by PT) will be considered a treatment-emergent AE (TEAE) if started after first study drug dose administration and no later than last study drug dose date + 30. AEs reported on Day 1 based on pre-dose findings (e.g., clinically significantly abnormal vital signs, laboratory test results, or electrocardiogram parameters) will not be considered as TEAEs.

The event counts and the number and percentage of subjects reporting TEAEs will be tabulated by SOC and PT; and by SOC, PT, and maximum severity. If more than 1 AE occurs with the same PT for the same subject, the subject will be counted only once for that PT using the most severe occurrence for the summarization by severity to study drug. In addition, the event counts and the number and percentage of subjects with TEAEs classified by the Investigator as related to the study drug, with most frequently reported TEAEs (PTs reported by $\geq 5\%$ of subjects), with treatment-emergent serious AEs (TESAEs), with fatal AEs (i.e., events that cause death), and with TEAEs leading to discontinuation of study drug will be summarized by SOC and PT. These tables will be sorted alphabetically by SOC and then by descending subject frequency for the PTs within each SOC.

The event counts and the number and percentage of subjects with any TEAEs will also be tabulated by PT without SOCs and will be sorted by descending subject frequency.

An AE listing by subject will display all events, including those which are not treatment-emergent, and will include the verbatim term in addition to the MedDRA SOC and PT. This listing will also include all relevant eCRF data associated with the event: e.g., date of onset, date resolved, date of first dose, date of last dose, study dose level at AE onset, severity, frequency, outcome, relationship to study drug, action taken with study drug, and required therapy. When a date is presented, the study day associated with the date will also be displayed. Separate listings will be presented for subjects with SAEs, subjects with AEs leading to discontinuation, and subjects who died (if any). In these listings, an indicator for treatment-emergent events will also be included.

14.2 Clinical Laboratory Variables

Laboratory evaluations will be completed according to the schedule presented in Table 3 below.

Table 3 Clinical Laboratory Assessments

Visit	Tests ^{a,b,c}
Screening	Clinical chemistry serum (including HbA1c, TSH, free T4 reflex), complete blood count, urinalysis, urine toxicity screen, and serum pregnancy test
Baseline	Clinical chemistry serum, complete blood count, urinalysis, urine toxicity screen, and urine pregnancy test
Week 8/ET	Clinical chemistry serum (including HbA1c), complete blood count, urinalysis, and urine pregnancy test

^a Pregnancy tests are only required for women of child-bearing potential.

^b An HbA1c test is only required at Screening and Week 8/ET.

^c TSH and free T4 reflex are only required at Screening.

Hematology tests include the following:

- Complete blood count (CBC) including:
 - White blood cell (WBC) count
 - Complete differential (relative and absolute)
 - Hematocrit (Hct), hemoglobin (Hgb), red blood cells (RBC), platelets
 - Reticulocyte count

Serum chemistry tests include the following:

- Sodium (Na), potassium (K), chloride (Cl), phosphorus (P), calcium (Ca), carbon dioxide (CO₂), blood urea nitrogen (BUN), creatinine (Cr), uric acid
- Alanine aminotransferase (ALT/SGPT), aspartate aminotransferase (AST/SGOT), gamma-glutamyl transpeptidase (GGT), alkaline phosphatase (ALP), total bilirubin (TBIL), lactate dehydrogenase (LDH)
- Glucose
- Albumin (ALB), total protein
- Prolactin
- HbA1c
- Lipid panel
 - Total cholesterol, high-density lipoprotein (HDL)-cholesterol, triglycerides, low-density lipoprotein(LDL)-cholesterol
- Thyroid stimulating hormone (TSH) and reflex free thyroxine (T4) (TSH and T4 are collected only at Screening)

Urinalysis tests include the following:

- Color, clarity, blood, RBCs, WBCs, protein, glucose, ketones, specific gravity, pH, leukocyte esterase, nitrite, microscopic analysis

Pregnancy tests include the following:

- A serum pregnancy test will be performed at Screening for women of child-bearing potential

- A urine pregnancy test will be performed at Baseline and Week 8/ET for women of child-bearing potential

All laboratory test results (including urine drug screen) are from a central laboratory and will be listed. The listings will include date and study day of collection. All units will be displayed in Système International [SI] units. Out-of-range values will be flagged in the data listings (e.g. 'L' or 'H').

Clinical laboratory values for hematology, chemistry and urinalysis (specific gravity and pH) will be summarized by descriptive statistics at Baseline and Week 8 visits. The change from Baseline values will also be summarized at the Week 8 visit. The overall minimum and maximum post-Baseline observed and change from Baseline values will also be summarized. For hemoglobin, hematocrit, and uric acid, the above summaries will be presented for each gender as well as for both genders combined. For urinalysis with categorical results (e.g., blood, protein, glucose, and ketones), the number and percentage of subjects will be tabulated by category at Baseline and Week 8, and the denominator is the number of subjects with non-missing values for the given parameter and visit.

Laboratory values (except for those that were only assessed at Screening or Baseline) will also be summarized in shift tables to determine the number and percentage of subjects with values classified as below (low), within (normal), and above (high) normal ranges at Week 8, overall post-Baseline minimum, and overall post-Baseline maximum. For the by-visit shift summary, the denominator is the total number of subjects with non-missing values at Baseline and the given visit for the given parameter. For the shift to the overall post-Baseline minimum or maximum, all post-Baseline values will be considered, including unscheduled and out of window values. The denominator is the number of subjects with non-missing Baseline and at least one post-Baseline value for the given parameter. For hemoglobin, hematocrit, and uric acid, the shift summaries will be presented for each gender and for both genders combined.

The number and percentage of subjects with potentially clinically important laboratory values (PCI) at Week 8 and overall post-Baseline will be summarized for selected parameters by Baseline status (All subjects and Within Normal Range). PCI criteria are listed in [Table 4](#) and [Table 5](#). For the overall post-Baseline summaries of PCI values, all post-Baseline values will be considered, including unscheduled and out of window values. Subjects with multiple PCI values for a given parameter will be counted only once for that parameter. For the by-visit summary, the numerator for the percentage is the total number of subjects with a post-Baseline PCI value for the given parameter and visit, and the denominator is the total number of subjects with non-missing values for the given parameter and visit. For the overall post-Baseline summary, the numerator for the percentage is the total number of subjects with

at least 1 post-Baseline PCI laboratory value for the given parameter, and the denominator is the number of subjects with at least 1 post-Baseline laboratory value for the given parameter. Subjects with any PCI values will be presented in an additional listing.

Table 4 Criteria for Potentially Clinically Important Laboratory Values – Hematology and Chemistry

Analyte	Conventional Unit	Low PCI Criteria	High PCI Criteria	SI Unit	Low PCI Criteria	High PCI Criteria
Hematology (whole blood)						
Hemoglobin (male)	g/dL	<11	>18	g/L	<110	>180
Hemoglobin (female)	g/dL	<10	>17	g/L	<100	>170
Hematocrit	%	<30	>50 (F) >55 (M)	L/L	<0.3	>0.5 (F) >0.55 (M)
Leukocyte (White Blood Cell Count)	$\times 10^3/\mu\text{L}$	≤ 2.8	≥ 15	$\times 10^9/\text{L}$	≤ 2.8	≥ 15
Neutrophils	$\times 10^3/\mu\text{L}$	≤ 1.5	No upper limit	$\times 10^9/\text{L}$	≤ 1.5	No upper limit
Platelet Count	$\times 10^3/\mu\text{L}$	≤ 75	≥ 700	$10^9/\text{L}$	≤ 75	≥ 700
Chemistry (serum or plasma)						
ALT (SGPT)	U/L	No lower limit	$\geq 3 \times \text{ULN}$	U/L	No lower limit	$\geq 3 \times \text{ULN}$
AST (SGOT)	U/L	No lower limit	$\geq 3 \times \text{ULN}$	U/L	No lower limit	$\geq 3 \times \text{ULN}$
Total Bilirubin	mg/dL	No lower limit	$\geq 1.5 \text{ ULN}$	umol/L	No lower limit	$\geq 1.5 \text{ ULN}$
BUN	mg/dL	No lower limit	≥ 30.0	mmol/L	No lower limit	≥ 10.71
Sodium	mEq/L	≤ 125	≥ 155	mmol/L	≤ 125	≥ 155
Potassium	mEq/L	≤ 3.0	≥ 5.5	mmol/L	≤ 3.0	≥ 5.5
Calcium, total	mg/dL	<8.0	>11.0	mmol/L	<2.0	>2.75
Lactate Dehydrogenase (LDH)	U/L	No lower limit	$\geq 3 \times \text{ULN}$	U/L	No lower limit	$\geq 3 \times \text{ULN}$
Alkaline Phosphatase	U/L	No lower limit	$\geq 3 \times \text{ULN}$	U/L	No lower limit	$\geq 3 \times \text{ULN}$
Uric acid (male)	mg/dL	No lower limit	≥ 10.5	umol/L	No lower limit	≥ 624.75
Uric acid (female)	mg/dL	No lower limit	≥ 8.5	umol/L	No lower limit	≥ 505.75
Albumin	g/dL	≤ 2.6	≥ 6.0	g/L	≤ 26	≥ 60
Total Protein	g/dL	≤ 5.0	≥ 10.0	g/L	≤ 50	≥ 100
Chloride	mEq/L	≤ 85	≥ 120	mmol/L	≤ 85	≥ 120
Glucose (random)	mg/dL	≤ 45.1	≥ 200.0	mmol/L	≤ 2.48	≥ 11
Serum Creatinine	mg/dL	Not Applicable	$>1.5 \text{ ULN}$	umol/L	Not Applicable	$>1.5 \text{ ULN}$
Triglycerides	mg/dL	Not	>300	mmol/L	Not	>3.39

		Applicable			Applicable	
Gamma-Glutamyl Transferase (GGT)	U/L	Not Applicable	≥3 ULN	U/L	Not Applicable	≥3 ULN

Table 5 Criteria for Potentially Clinically Important Laboratory Values - Urinalysis

Urinalysis (qualitative dipstick)	Low PCI Criteria	High PCI Criteria
Blood (occult blood)	Not Applicable	≥+2
Protein	Not Applicable	≥+2
Glucose	Not Applicable	≥+2

The pregnancy results (positive or negative) for female subjects will be presented in a listing.

14.3 Vital Signs

Vital signs are assessed at Screening, Baseline, and Weeks 2, 4, 6 and 8/ET visits.

Vital signs including weight, height (only at Screening), and derived BMI will be summarized at Baseline and all post-Baseline visits using descriptive statistics. The change from Baseline values will also be summarized at each post-Baseline visit.

Vital sign values will be considered PCI if they meet both the observed value criteria and the change from baseline criteria listed in [Table 6](#). The number and percentage of subjects with post-Baseline vital signs that are PCI will be summarized at each post-Baseline visit and for overall post-Baseline. For the overall post-Baseline summaries, all post-Baseline values will be considered, including unscheduled and out of window values. Subjects with multiple PCI values for a given parameter will be counted only once for that parameter. For the by-visit summary, the numerator for the percentage is the total number of subjects with a post-Baseline PCI vital sign for the given parameter and visit, and the denominator is the total number of subjects with non-missing values for the given parameter and visit. For the overall post-Baseline summary, the numerator for the percentage is the total number of subjects with at least 1 post-Baseline PCI vital sign for the given parameter, and the denominator is the number of subjects with at least 1 post-Baseline vital sign for the given parameter. A listing of all subjects with any PCI values will be provided.

Table 6 Criteria for Potentially Clinically Important Vital Signs

Vital Sign Parameter	Unit	Criteria ^a		
		Observed Value	And/Or	Change Relative to Baseline
Systolic blood pressure (supine or sitting)	mmHg	≥180	And	Increase of ≥20
		≤90	And	Decrease of ≥20
Diastolic blood pressure (supine or sitting)	mmHg	≥105	And	Increase of ≥15
		≤50	And	Decrease of ≥15
Pulse (supine or sitting)	bpm	≥120	And	Increase of ≥15
		≤50	And	Decrease of ≥15
Weight	kg	Not Applicable		Increase of ≥7%
				Decrease of ≥7%

^a A post-Baseline value is considered a PCI value if it meets both criteria for observed value and change from baseline.

14.4 Electrocardiogram

12-lead ECG assessments are performed at Screening, Baseline, Week 2 and Week 8/ET visits. ECGs will be completed in triplicate at Screening, and as a single tracing at all other timepoints. When ECG is collected in triplicate, the average of the triplicate will be considered as one assessment for the analyses. All tracings will be evaluated by a central reading laboratory. ECG data summaries will be performed using the centrally evaluated data, including the cardiologist's interpretation.

Observed values of ECG variables (heart rate, PR interval, RR interval, QRS interval, QT interval, and QTc intervals) and the changes from baseline at each assessment timepoint will be summarized by visit. QTc intervals include QTcB (Bazett's formula) and QTcF (Fridericia's formula).

QTcF (msec) observed and change from Baseline values will also be classified into the following categories, and the number and percentage of subjects in each category will be summarized at each visit and for the overall post-baseline maximum:

- Observed
 - ≤450, 451 to 480, 481 to 500, and >500
 - >450
 - >480
- Change from Baseline
 - ≤10, 11 to 30, 31 to 60, and >60
 - >30

Electrocardiogram variable values will be considered PCI if they meet or exceed the upper limit values listed in Table 7. The number and percentage of subjects with post-baseline PCI values will be summarized at each post-Baseline visit and for overall post-Baseline. For the by-visit summary, the numerator for the percentage is the number of subjects with a post-Baseline PCI ECG for the given parameter and visit, and the denominator is the number of subjects with non-missing values for the given parameter and visit. For the overall post-Baseline summary, the numerator for the percentage is the number of subjects with at least 1 post-Baseline PCI ECG for the given parameter, and the denominator is the number of subjects with at least 1 post-Baseline ECG for the given parameter. A listing of all subjects with any PCI values will be provided.

Table 7 Criteria for Potentially Clinically Important ECG Values

ECG Parameter	Unit	High PCI Criteria
QRS Interval	msec	≥ 120
PR Interval	msec	≥ 220
QTcB or QTcF	msec	>500
QTcB or QTcF: change from Baseline	msec	>60

For cardiologist's interpretations, the number and percentage of subjects with ECG results that are determined as normal or abnormal will be summarized at scheduled visits. The overall post-baseline worst interpretation will also be summarized (i.e. if a subject has one or more ECG results that is/are considered as abnormal, this subject will be counted in the abnormal category). Cardiologist's interpretations will also be summarized in a shift table to determine the number and percentage of subjects with ECG results classified as normal or abnormal at scheduled post-Baseline visits relative to the same classification at the Baseline visit. The shifts from Baseline to overall post-Baseline worst interpretation will also be presented. For the by-visit shift summary, the denominator is the number of subjects with non-missing cardiologist's interpretation at Baseline and the given visit. For the summaries of shift from Baseline to the overall post-Baseline worst interpretation, the denominator is the number of subjects with non-missing Baseline and at least 1 post-Baseline cardiologist's interpretation.

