#### 4.3 Exclusion Criteria

1. Use of an antipsychotic within 3 weeks or 5 half-lives of Baseline (whichever is longer)
2. Has greater than New York Heart Association (NYHA) Class 2 congestive heart failure or Class 2 angina pectoris, sustained ventricular tachycardia, ventricular fibrillation, or torsade de pointes, or syncope due to an arrhythmia
3. Had a myocardial infarction within the 6 months prior to Screening
4. Has a known personal or family history or symptoms of long QT syndrome
5. Has any of the following ECG results at Screening (the ECG may be repeated once at Screening in consultation with the Medical Monitor):
  - a. If the subject is not on citalopram, escitalopram, or venlafaxine
    - i. QTcF >450 ms, if QRS duration <120 ms
    - ii. QTcF >470 ms, if QRS duration ≥120 ms
  - b. If the subject is on citalopram, escitalopram, or venlafaxine
    - i. QTcF >450 ms, if QRS duration <120 ms
    - ii. QTcF >450 ms, if QRS duration ≥120 ms
6. Has clinically significant laboratory abnormalities that, in the judgment of the Investigator or Medical Monitor, would jeopardize the safe participation of the subject in the study
7. Evidence of severe or medically significant hepatic or renal impairment on laboratory tests as assessed by the Investigator or Medical Monitor
8. Has uncontrolled diabetes or a glycosylated hemoglobin (HbA1c) >8% at Screening

9. Has laboratory evidence of hypothyroidism at Screening, as measured by thyroid-stimulating hormone (TSH) and reflex free thyroxine (T4). If TSH is abnormal and the reflex free T4 is normal, the subject may be enrolled
10. Has a body mass index (BMI) of <19 or >35
11. Has a known history of a positive hepatitis B virus (HBV), hepatitis C virus (HCV), or human immunodeficiency virus (HIV) test
12. Has a history of PD psychosis, schizophrenia, or other psychotic disorder, or bipolar I or II disorder. Subjects who are currently being treated for eating disorder, obsessive-compulsive disorder (OCD), attention deficit hyperactivity disorder (ADHD), panic disorder, acute stress disorder, or posttraumatic stress disorder (PTSD), according to DSM-5 criteria, are also not eligible.
13. Has a current diagnosis of delirium
14. Has a current primary diagnosis of borderline, antisocial, paranoid, schizoid, schizotypal, or histrionic personality disorder, according to DSM-5 criteria

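### ECG PCI counts for QRS and PR (and, more narrowly, QTcF >450 ms) take no account of Baseline, so stable pre-existing conduction delay is counted as a post-Baseline finding

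*SAP*

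**What the plan says.** SAP 14.4 sets the rule: "Electrocardiogram variable values will be considered PCI if they meet or exceed the upper limit values listed in Table 7". Two rows of Table 7 are absolute limits on the observed interval: "QRS Interval msec ≥ 120" and "PR Interval msec ≥ 220". The only row that refers to the subject's own starting value is "QTcB or QTcF: change from Baseline", with a limit of >60 ms. PCI is tabulated for each post-Baseline visit and overall. For the overall count, "the denominator is the number of subjects with at least 1 post-Baseline ECG for the given parameter". Nothing is conditioned on, or split by, Baseline.

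The same section classifies observed QTcF into absolute categories, including >450 ms, at each visit and for the highest post-Baseline value.

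On entry, exclusion 5 (Protocol 4.3) sets QTcF limits that depend on QRS. For subjects not on citalopram, escitalopram or venlafaxine, one limit reads "QTcF >470 ms, if QRS duration ≥120 ms". The criterion is applied to the Screening ECG. No PR limit is listed.

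The SAP treats its other PCI measures differently. Under SAP 14.2, laboratory PCI counts "will be summarized for selected parameters by Baseline status (All subjects and Within Normal Range"). Under SAP 14.3, "Vital sign values will be considered PCI if they meet both the observed value criteria and the change from baseline criteria".

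**The concern.** The protocol's QTcF limits anticipate subjects who enter with QRS ≥120 ms, and the SAP uses the same cut-off to call a post-Baseline QRS potentially clinically important. A subject with a stable QRS of 130 ms is thus a PCI case at Week 2, at Week 8 and overall, with no change. The same can happen with PR, which eligibility does not restrict.

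The study has one arm, so no control group shows the background count. Each subject's Baseline is the only reference available, and these counts do not use it. A reader of the safety table could take a count made up largely of entry characteristics as a finding that arose on treatment.

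**Working it through.** **1. The three PCI rules side by side**

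| Domain | Observed value | Change from Baseline required | Split by Baseline status |
|---|---|---|---|
| Laboratory (SAP 14.2) | yes | no | yes |
| Blood pressure and pulse (SAP 14.3) | yes | yes | no |
| QRS, PR (SAP 14.4, Table 7) | yes | no | no |

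The ECG intervals are the exception, and the SAP gives no reason.

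**2. Who can enter already over the limit**

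- QRS ≥120 ms: eligible, subject to the QTcF limit.
- PR ≥220 ms: eligible; there is no PR criterion.
- QTcF 451 to 470 ms at Screening: eligible only if QRS is ≥120 ms and the subject takes none of the three named antidepressants.
- QTcF above 450 ms at Baseline: also possible in others, because exclusion 5 is tested at Screening, while the Baseline ECG is a separate single tracing.

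For subjects on the three antidepressants with QRS <120 ms, Protocol 4.3 gives a QTcF limit of 450 ms, whereas the synopsis and Appendix A give 425 ms. Those passages must be reconciled, but neither version alters this point.

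**3. The denominator**

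The plan's sample size (SAP 3.5) reproduces. With mean change 3, SD 6.0, two-sided 0.05 and a paired t-test, power is 0.795 at n = 33 and 0.808 at n = 34. Then 34 / (1 − 0.15) = 40. I take N = 40 as an approximate denominator.

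**4. Size of the effect**

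The documents give no Baseline prevalence p of QRS ≥120 ms or PR ≥220 ms, so p is an assumption. If every pre-existing case persists and the drug has no effect, the expected count for one parameter is 40 × p, and the chance of at least one such count is 1 − (1 − p)^40.

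| Assumed p | Expected count | Chance of at least one |
|---|---|---|
| 2% | 0.8 | 55% |
| 5% | 2 | 87% |
| 10% | 4 | 98.5% |
| 15% | 6 | 99.8% |
| 20% | 8 | >99.9% |

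With a split, these subjects contribute nothing to the group below the limit at Baseline. At p of 5% to 15% that group has 40 − 2 = 38 to 40 − 6 = 34 subjects.

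**5. QTcF >450 ms at the post-Baseline maximum**

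Two post-Baseline ECGs are scheduled (Weeks 2 and 8). Assume a normal within-subject SD of 8 to 12 ms and no drug shift. For a subject whose usual value is 455 ms, the chance that one tracing exceeds 450 ms (cut at 450.5) is p1 = 1 − Φ((450.5 − 455)/SD), and the chance that the higher of two does is 1 − (1 − p1)². This gives 92% at SD 8 and 88% at SD 12. Such a subject is very likely to be counted without any change.

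For a usual value of 440 ms the same formula gives 18% and 35%. A Baseline split therefore removes pre-existing cases but not random crossings, and the resulting new-onset count is not a pure drug effect.

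**The case against.** The strongest reply is that the PCI table is not the output meant to show change. SAP 14.4 also plans change-from-Baseline summaries by visit for all intervals, including PR and QRS. It plans QTcF change categories at each visit and for the post-Baseline maximum, a PCI row for QTc change >60 ms, a normal/abnormal shift table, and a listing of every PCI subject. With about 40 subjects, pre-existing cases can be found by hand. The SAP calls the count post-Baseline, not treatment-emergent, and a pooled count is a legitimate description.

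Much of this stands, and it rules out several stronger readings:

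- A reader might infer that the plan cannot show whether treatment changed conduction or repolarisation. It can, through the change summaries and categories. QT, the cardiac effect that the protocol quantifies (about 5 to 8 ms in Parkinson's disease psychosis, 9.4 ms in the Alzheimer's disease psychosis study), is the parameter that already has a Baseline reference. The protocol describes no QRS or PR signal.
- A reader might infer that QTcF up to 470 ms is generally eligible. It is eligible at Screening only under the two conditions in step 2. The >450 ms category is also shown at each visit, which may include Baseline, so a group-level reference may exist.
- A reader might want every QTc threshold split. Exclusion 5 bars Screening QTcF above 470 ms in every group, so >480 and >500 ms have almost no target, and Baseline status has no meaning for a change criterion.
- A reader might compute an overstatement factor, for example 3/40 = 7.5% against 1/38 = 2.6%. That rests on an assumed prevalence and exactly one assumed new case, so it estimates nothing in this plan.

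The reply does not close the gap. Mean changes can hide individual crossings. The shift table is not interval-specific: a subject read as abnormal at Baseline stays abnormal whatever QRS or PR does. A listing leaves the new-onset count to the reader.

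**Conclusion.** The point holds for QRS and PR, and in a narrower form for QTcF >450 ms at the post-Baseline maximum. As written, the PCI counts combine pre-existing and new findings, and no planned output gives a new-onset QRS or PR count.

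If 5% to 15% of 40 subjects enter over a limit and stay there, about 2 to 6 subjects per parameter would be counted with no drug effect. That prevalence is an assumption, and a true value near zero would make the issue negligible. The effect is confined to descriptive safety tables; the primary analysis is untouched. This is an inexpensive improvement, not a flaw that undermines the safety evaluation.

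A lesser wording point: the text of SAP 14.4 includes values equal to the limit, while Table 7 prints > for the QTc rows. Values of exactly 500 ms, or a change of exactly 60 ms, are PCI by the text and not by the table.

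**What to change.** In SAP 14.4, present QRS PCI, PR PCI and the observed QTcF >450 ms category twice, following the layout of SAP 14.2: for all subjects, and for subjects not meeting that criterion at Baseline. Label the second as the new-onset count, with its own denominator. Leave QTcF >480 ms, QTc >500 ms and QTc change >60 ms as they are. Make the comparison signs in the text and Table 7 agree.

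The cost is a short SAP wording change and one extra row or column in tables already planned. Baseline is defined in SAP 5.3 and the ECGs are already scheduled, so no new data are needed. The drawback is a somewhat smaller denominator in the second group, in a study that is already small.
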